## Recruitment

Women were recruited from Black church congregants that are known to have a high proportion of Black females, from businesses such as hair salons, Black sororities, and community events. Recruitment methods included flyers, announcements on websites using the flyer, presentations, follow-up phone calls, and face-to-face meetings with church leaders, congregants, business owners, sororities, and community members. Those interested in participating in the study were instructed to contact the research staff (PI or trained RAs) who are registered nurses, via telephone or email. The PI or RA conducted either a face to face or telephone screening interview. After an explanation of the study and answering questions, potential participants were (1) screened for inclusion/exclusion; (2) uncontrolled BP (systolic and/or diastolic greater than or equal to 130/80 but less than 160/100 mmHg; interviewees had their BP checked and reported the numbers when called for screening; BP was taken later to confirm eligibility before the consent form was signed and baseline data collected); and (3) ability to participate in physical activity using the Physical Activity Readiness Questionnaire (PAR-Q). Those who were eligible and agree to participate in the study were visited by the PI or RA at their home or another preferred private location. At that time, the participants BP was taken to confirm eligibility for the study. If the BP criteria was met, the participant provided informed consent and baseline data were obtained. If the BP criteria were not met, participants were thanked for their time and told that any collected information during the screening process would be discarded by shredding.

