## Technology

After completing the CDSMP sessions, study participants were randomly assigned to either the treatment (ITEC) or the control arm (IT).

The technology component of the study was linked to Fitbit Plus, a cloud-based collaborative care platform that was designed to store and track data. The PI was trained in the Fitbit Plus platform, synchronizing data collection devices, instructing participants in the use of equipment, monitoring participant data, and interactive coaching messages. In the privacy of their homes, or another preferred location, each study participant received individualized instruction (about 45 to 90 minutes) to Fitbit Plus and all study tools accommodating various technological skills.

Study equipment included three wireless tools (Omron BP monitor, Fitbit activity tracker, and Fitbit weight scale) and five apps (Omron Connect, Fitbit, MyFitnessPal, Apple Health if iPhone user or Google Fit if android user, and Fitbit Plus). Apps were installed and tools synchronized to the participant’s smartphone. Apple Health and Google Fit allowed Fitbit Plus to import app data from Fitbit, MyFitnessPal, and Omron. Participant action plans were set up in Fitbit Plus to correspond to the study aims. As participants wore their Fitbit activity tracker, took their BP, stepped onto the weight scale, or entered food intake, their measurement data were transmitted in real time via Wi-Fi and Bluetooth Smart technology to the Fitbit Plus dashboard. In the dashboard, participants could view their data along with the PI. Two exceptions were the manual BP recording for Android users and the manual self-reported medication-taking for all participants, as described under Fitbit Plus Measures. The PI monitored all study participant data during a two-week trial period to allow participants an opportunity to adapt to using the wireless tools and apps. Once the orientation period was over, data were monitored via the Fitbit Plus platform for study purposes.

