All baseline manual measurements and study questionnaires were repeated at 3, 6, and 9 months. All other data were collected through the Fitbit Plus Platform via wireless tools. Personal contact every three months for about 30 minutes provided a human element to the Fitbit Plus technology component and allowed the PI to troubleshoot any problem areas or equipment issues.

Gift cards were given to participants for time expended for baseline assessment (\$20) and repeated measures at 3- (\$30), 6- (\$40), and 9-months (\$60) totaling \$150.

If study participants completed all parts of the research study, then as a completion bonus, they were allowed to keep all measurement tools including the blood pressure monitor, Fitbit, and weight scale, along with the CDSMP book at the conclusion of the study. After Fitbit Plus access ended, participants were able to continue to monitor themselves through the corresponding apps on their smartphone. For those study participants who do not complete the study, the blood pressure monitor, Fitbit, weight scale, and book were returned to the PI when they exited the study.

At the completion of the study, Fitbit Plus transmitted a copy of all collected data at the request of the PI. Both the PI and study participants instructed Fitbit Plus to delete all study participant data when the study ended.

A summary of the overall results of the project in ‘lay’ language was shared with participants in their preferred format (such as email, letter, or in-person) while ensuring confidentiality of individual responses after the study has ended.

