### Statistical Analysis Plan

**Sample size and power.** All participants meeting study eligibility requirements received the CDSMP classes for 6 weeks. Participants from this pool were randomized to the treatment arm (with ITEC and electronic devices such as the home BP monitoring, weight scale, and physical activity tracker), and the control arm, with IT monitoring only. Our sample of  $n=45$  participants per arm ( $N=90$  in total), measured at baseline, and at 3-, 6-, and 9-months post CDSMP, has approximately 80% power (assuming 5 dropouts per arm) to detect an effect size of  $\sim 0.205$  or greater at the  $\alpha=0.05$  level of statistical significance, given a realistic range of simulated unstructured covariance matrices. Assuming an 11% rate of attrition, the enrollment target was set at 90 for both arms, which would yield a final sample of 80 participants, or 40 per arm.

**Statistical analysis.** A hierarchical, mixed-effects repeated measures design was used to analyze the primary and secondary outcomes of interest. This model, which allows for heterogeneous variances across time points, is preferred over a simple univariate model that requires compound symmetry (i.e., the correlation between a measurement at time  $T_i$  and any other measurement within the same patients at  $T_j$ , is equal for all  $i$  and  $j$ ). A mixed-effects model is more efficient for handling missing at random (MAR) data than, for example, a generalized estimating equations (GEE) repeated measures approach, which requires the more restrictive assumption that missing data are missing completely at random (MCAR). We performed a sensitivity analysis using both a GEE model and sequential application of the EM algorithm to impute missing data. Data from participants ( $n=7$ ) who dropped out of the study before their first post-CDSMP visit were not included in the analysis. However, baseline information for these participants were compared with participants who continued in the study.

When appropriate a constrained longitudinal data analysis (cLDA) model was used, assuming the same baseline mean for treatment and referent arms with missing baseline data. The cLDA model examines treatment differences over time. Coffman et al. (2016) cite the cLDA as the method of choice for longitudinal RCTs because it yields robust estimates of treatment effect differences under reasonable missing data assumptions.

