Both models are valid for repeated measures if data are missing at random (MAR). Little's test was used to determine if variables were missing completely at random (MCAR) while significant covariate-dependent missing values were identified by regressing a dichotomous indicator variable for missingness against key models factors. (Li, 2013) That is, if the missing values were non-randomly associated with the latter variables of interest, the mechanism was deemed to be missing at random (MAR). A sampling of observed vs. non-unobserved items were subjectively scrutinized for signs of a 'missing not at random (MNAR)' pattern for the data. Overall, no relevant violation of the MAR assumption was evident in our analyses.

Descriptive statistics were used to summarize demographic data (such as marital status, education, and income) of study participants.

An independent (unpaired) samples t-test was used to determine the difference between the means of the treatment and referent groups. The dependent (paired) sample t-test was used to determine the mean differences between variables (systolic and diastolic BP and weight/BMI) for treatment and referent group participants from baseline (post-CDSMP) to month 3, from month 3 to 6, and from month 6 to 9. Time frames were allotted to further participant engagement in self-management.

The use of a two-sample t-test versus non-parametric methods for nonnormally distributed data has been debated in the literature (le Cessie et al., 2020). In general, the former is reasonable robust to departures from normality, providing that the sample sizes are sufficiently large, and the underlying variances are finite (with no extreme outliers) (Lumley et al., 2002)

All data collection tools (except the Hill-Bone CHBPTS medication subscale) were converted to a 100-point scale to enable comparison. Questionnaire scores were analyzed for changes across several time points using a mixed-effects repeated measures model for both groups. In comparison to a repeated measures ANOVA test, the mixed model tends to yield valid estimates of treatment effects even when the missing values are not completely missing at random (Detry & Ma, 2016). Rounding was based upon significant digits rather than a fixed number of decimal places (i.e., Goldilocks method) (Efird, 2021). Data were analyzed using SAS - v 9.4 (Cary, NC).

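### The SAP ties its common-baseline (cLDA) model to missing baseline data, although outcomes measured before randomisation gain precision from it with complete baselines and device outcomes have no baseline that would justify it

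*Combined protocol and SAP*

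**What the plan says.** The statistical analysis paragraphs of the Statistical Analysis Plan set the default: "A hierarchical, mixed-effects repeated measures design was used to analyze the primary and secondary outcomes of interest". They then allow an alternative where appropriate: a cLDA (constrained longitudinal data analysis) "model was used, assuming the same baseline mean for treatment and referent arms with missing baseline data". No other condition for cLDA is given and no outcome is assigned to it. Shortly afterwards the SAP reports that the authors of a cited methods paper "cite the cLDA as the method of choice for longitudinal RCTs", a recommendation not limited to trials with missing baselines. The SAP next speaks of both models, so the default is something other than cLDA. A later paragraph names the mixed-effects model again for questionnaire scores. Adjustment for baseline as a covariate is not mentioned anywhere.

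On timing, the Recruitment section says: "If the BP criteria was met, the participant provided informed consent and baseline data were obtained". The Baseline data section adds height, weight and the questionnaires at that visit, and Baseline and Repeated Measures adds waist circumference. The CDSMP section puts the workshop after baseline collection, and the Technology section puts randomisation after the workshop. The Fitbit Monitoring section states: "All baseline manual measurements and study questionnaires were repeated at 3, 6, and 9 months". Everything else comes through Fitbit Plus. Device set-up is described after randomisation, and controls received devices only after month 3.

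Two passages leave the BP analysis unsettled. The t-test paragraph of the SAP runs its comparisons "from baseline (post-CDSMP) to month 3, from month 3 to 6, and from month 6 to 9", although no manual visit between the workshop and month 3 is described as a baseline. Manual BP is presented as a check on the Omron readings, while change in BP is listed as studied under the Omron monitor.

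**The concern.** In a randomised trial, the arms share one true mean on anything measured before allocation. cLDA uses that fact. It keeps baseline in the outcome vector, fits one baseline mean, and lets the arms differ only afterwards. The gain comes from the correlation between baseline and follow-up and is present when every baseline value is observed. Making missing baseline data the condition therefore separates the method from its main benefit.

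Read plainly, the condition would not reach the outcomes best suited to the method, because BP was checked at enrolment to confirm eligibility and the other manual measures and questionnaires were taken at the same visit. The outcomes that do lack a baseline are those first recorded on devices issued after allocation. For these, randomisation says nothing about a common starting mean.

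Two things are at stake. One is precision on BP with about 40 women per arm. The other is an open choice: without a stated rule for what counts as appropriate, two models with different standard errors are available for the same outcome.

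**Working it through.** **The plan's own figures.** 80 / (1 − 0.11) = 89.9, so 90 enrolled and 40 completers per arm reproduce (5/45 = 11.1%). The stated power of about 80% for an effect size near 0.205 can be neither confirmed nor refuted, because the effect-size metric and the simulated covariance matrices are not given. The point does not depend on it.

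**Inputs.** n = 40 per arm and α = 0.05 are from the SAP; two-sided testing and 80% power give the multiplier 1.96 + 0.84 = 2.80. The baseline-to-follow-up correlation ρ is not in the documents and is assumed to be 0.3 to 0.7, with equal variances σ² at each visit.

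**Variance of the arm difference at one follow-up visit, complete data.**
- Difference in change scores (separate baseline means): 4σ²(1 − ρ)/n
- Difference in visit means (baseline ignored): 2σ²/n
- cLDA: 2σ²(1 − ρ²)/n

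The ratio of cLDA to change scores is (1 − ρ²)/[2(1 − ρ)] = (1 + ρ)/2. The ratio of cLDA to visit means is 1 − ρ². With n = 40, in units of σ²:

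| ρ | Change | Visit mean | cLDA | cLDA/change | cLDA/visit mean | Detectable difference in SD: change, cLDA |
|---|---|---|---|---|---|---|
| 0.3 | 0.0700 | 0.0500 | 0.0455 | 0.65 | 0.91 | 0.741, 0.597 |
| 0.5 | 0.0500 | 0.0500 | 0.0375 | 0.75 | 0.75 | 0.626, 0.542 |
| 0.7 | 0.0300 | 0.0500 | 0.0255 | 0.85 | 0.51 | 0.485, 0.447 |

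The detectable difference is 2.80 × √variance; for example 2.80 × √0.0700 = 0.741. Against change scores the standard error is 19%, 13% and 8% smaller (√0.65 = 0.806, √0.75 = 0.866, √0.85 = 0.922).

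**Allowing for the entry window.** Women enter with systolic BP of at least 130 and/or diastolic of at least 80, and below 160/100. This narrows the spread at baseline and makes equal variances unrealistic. A simulation of 1.5 million women per scenario assumed a long-run systolic mean of 128 to 140 mmHg, a between-woman SD of 13, a visit-to-visit SD of 7 to 10, correlated systolic and diastolic BP, and telephone and confirming readings both inside the window. It gave ρ of 0.40 to 0.64, a baseline SD of 9.4 to 11.3 and a follow-up SD of 11.1 to 14.0. The cLDA variance was 9 to 14% below change scores and 16 to 41% below visit means (1 − 0.40² = 0.84; 1 − 0.64² = 0.59). Using 2.80 × √(2V/40), the detectable systolic difference is:
- cLDA: 5.7 to 7.8 mmHg
- change scores: 5.9 to 8.3 mmHg
- visit means: 7.0 to 8.8 mmHg (2.80 × √(2 × 14.0²/40) = 8.8)

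Comparing the ends of the ranges, the gain over change scores is 5.9 − 5.7 = 0.2 to 8.3 − 7.8 = 0.5 mmHg. Repeat simulations with other assumed diastolic parameters agreed closely.

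**Baseline as a covariate.** If the default model already adjusts for a complete baseline, cLDA adds nothing.

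**Device outcomes.** If the control arm has no baseline at all, the information matrix for four visits and 40 per arm gives a cLDA variance of 0.050σ² for the post-baseline difference at ρ = 0.3, 0.5 and 0.7. That equals the follow-up-only value 2/40 = 0.050, so the constraint buys no precision.

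**The case against.** The strongest reply is that the SAP never says BP was analysed without the constraint, nor that steps, calories or app adherence were analysed with it. The words about missing baseline data can be read as describing what cLDA tolerates, and the proviso of appropriateness could exclude outcomes with no valid baseline. cLDA is itself a mixed-effects model, so naming that model for the primary outcomes does not rule it out. A reader might infer that the rule is the wrong way round, with BP given the weaker model and device outcomes the constrained one. The documents do not support that as a statement of fact, because neither assignment is written down.

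A reader might also infer that a BP baseline cannot be missing. That follows for the enrolment reading only. The t-test paragraph places baseline after the workshop, and completeness of such a reading cannot be judged from the documents. If the BP outcome is Omron BP, it falls among the outcomes without a pre-randomisation value.

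These limits stand, but they do not remove the point. The SAP treats the default and cLDA as two models, lists baseline among the repeated measurements and states no covariate adjustment, so analysis without the constraint is the natural reading for complete outcomes. The SAP's BP comparison from baseline to month 3 in both groups can rest only on manual BP, since controls had no devices in months 1 to 3.

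Finally, the SAP is written after the analysis: it reports seven early dropouts and a conclusion about missingness. A change of model now is post hoc. That is a real cost, and it governs how the change should be reported.

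**Conclusion.** The concern holds as a matter of efficiency and specification. The only stated condition for cLDA does not match the reason the SAP gives for preferring it. Outcomes measured before randomisation appear to be left without the constraint or any stated baseline adjustment, and device outcomes have no baseline for which randomisation would justify it.

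The size is modest. The realistic figure for systolic BP is the entry-window one, about 9 to 14% less variance than change scores. The equal-variance range of 15 to 35% less (ratios 0.85 to 0.65) is an upper guide. The gain is larger against an unadjusted comparison of visit means, and nil if baseline is already a covariate. All of this rests on assumed correlations and SDs, because the documents give none. Nothing here shows bias or an invalid test.

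The definition of baseline must be settled first. The constraint is justified for the enrolment reading. It would not be justified by randomisation for a reading taken after allocation.

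**What to change.** Replace the cLDA sentence in the SAP with a rule by outcome:
- **Measured before randomisation** (manual systolic and diastolic BP, manual weight/BMI, waist, Hill-Bone, SEMCD, Communication, SCHI): use cLDA whether or not baseline values are missing. Baseline and months 3, 6 and 9 form the outcome vector, with unstructured covariance, one common baseline mean and arm-by-time terms after baseline. The arm effect is the model contrast at each visit. Healthcare Utilization follows the same principle with a model suited to counts.
- **Device-only** (steps, calories, app-recorded adherence, Omron BP): do not apply the common-baseline constraint.
- Delete the proviso of appropriateness, so that the model follows from the outcome.
- State that manual BP is the source for any arm comparison that includes months 1 to 3.
- Reconcile the post-workshop baseline in the t-test paragraph with the pre-workshop baseline in the Recruitment, CDSMP and Fitbit Monitoring sections.

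The cost is about one SAP paragraph and a re-run on existing data, with no new collection. Because the analysis has already been done, label the cLDA results as a re-analysis and report them beside the model already fitted, stating how that model handled baseline.

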## Fitbit Monitoring

With smart monitoring of connected devices in Fitbit Plus, data were tracked, analyzed, and transparently displayed to provide opportunities for participants to better understand their condition and self-manage by being actively engaged in their own care. In the CDSMP, all participants were taught to write action plans and report if they were successful, partially successful, or not successful in achieving their plan based on participant self-tracking of their data. Fitbit Plus allowed real-time adherence tracking. If participants were adhering to their action plan, study measures displayed a green color indicating a positive trend and if they were not adhering, measures would display a red color indicating a negative trend, alerting the PI to communicate with participants and encourage active engagement in their self-care.

Only the treatment arm action plans were monitored with individualized coaching messages (ITEC) via secure text messaging in the Fitbit Plus dashboard with real-time participant feedback. Coaching messages focused on helping participant's problem-solve barriers to goal

achievement with relevant dialogue to encourage BP control, medication adherence, and lifestyle modifications (physical activity, caloric intake, and weight management). The PI sent tailored ITEC messages via Fitbit Plus to treatment arm participants weekly for months 1-3, biweekly for months 4-6, and no ITEC messages for months 7-9 (to assess for sustainability).

During months 1-3, the control arm received usual care only, along with monthly manual BP and weight measures. After that time, the control arm was given the same wireless tools and apps as the treatment arm. In addition, they received individualized instruction equivalent to the treatment arm and practiced using the tools during a two-week trial period. For months 4-9, the control arm was monitored with IT via Fitbit Plus with no coaching. Fitbit Plus was used only to track participants for comparative data with the treatment arm. The control participants were not contacted between data collection periods, except to send reminders if they were not participating in daily measures.

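### The conclusion that missingness did not violate MAR is unsupported: the formal checks can reject only MCAR, and no analysis examines a departure from MAR

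*Combined protocol and SAP*

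**What the plan says.** All of this is in the Statistical Analysis Plan, under the statistical analysis paragraphs.

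- **Main models.** These are a mixed-effects repeated measures model and, where appropriate, a cLDA model. The plan makes the validity of both conditional on MAR.
- **Formal checks.** Little's test is applied for MCAR, and a missingness indicator is regressed on key model factors. The rule for reading the regression is: "if the missing values were non-randomly associated with the latter variables of interest, the mechanism was deemed to be missing at random (MAR").
- **MNAR check.** "A sampling of observed vs. non-unobserved items were subjectively scrutinized for signs of a" pattern of data missing not at random. The plan gives no rule for choosing the items and no criterion for judging them.
- **Sensitivity analyses.** "We performed a sensitivity analysis using both a GEE model and sequential application of the EM algorithm to impute missing data". The plan describes GEE as an approach "which requires the more restrictive assumption that missing data are missing completely at random (MCAR").
- **Early leavers.** Seven participants "who dropped out of the study before their first post-CDSMP visit were not included in the analysis". Their baseline data were compared with those of women who continued.
- **Conclusion.** "Overall, no relevant violation of the MAR assumption was evident in our analyses".

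**The concern.** The conclusion is about MAR, but the formal evidence is about MCAR. Under the plan's rule, an association between missingness and observed factors is taken as showing MAR. MNAR data can show the same association, because the unseen outcome is correlated with the observed variables. Neither outcome of the regression can therefore point to MNAR, and everything rests on a subjective look without a criterion.

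The main models need MAR, so a reader will take the sentence as the warrant for the treatment estimates. What is at stake is a departure from MAR that differs between arms, since that biases the contrast. The Fitbit Monitoring section makes one possible: "The PI sent tailored ITEC messages via Fitbit Plus to treatment arm participants weekly for months 1-3, biweekly for months 4-6", while controls in those months had no coaching. Reasons for leaving could then differ by arm, and the bias could go either way.

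**Working it through.** **1. What each element can show**

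| Element | Null or assumption | Can it reveal a departure from MAR? |
|---|---|---|
| Little's test | MCAR | No; it can reject MCAR only |
| Missingness regression | No association with observed factors | No; an association fits both MAR and MNAR |
| Look at a sample of items | None stated | Not assessable; no criterion |
| GEE | MCAR, in the plan's own words | No; it assumes more than MAR |
| EM imputation | Normally MAR | No; same assumption as the main models |

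The documents contain no delta-adjusted, tipping-point, pattern-mixture, selection-model or reference-based analysis.

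**2. Simulation of the two formal checks**

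Assumed inputs: 45 per arm, 4 visits, SD 1, exchangeable correlation 0.3, 0.5 or 0.7, about 11% missing at month 9 in both arms, logistic slope 2 and about 500 runs per case.

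- Under MAR, at least one check rejected in 97-98% of runs, and the EM estimate of the contrast was unbiased.
- Under MNAR, at least one check rejected in 35%, 61% and 83% of runs at correlations 0.3, 0.5 and 0.7. In the other 65%, 39% and 17%, both checks passed MNAR data.
- Where the regression rejects under MNAR, the plan's rule labels the data MAR.

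With equal MNAR dropout in both arms the bias in the contrast was about 0, so harm depends on a difference between arms.

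**3. The plan's own attrition figure**

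5/45 = 11.1%, and 80/(1 - 0.11) = 89.9, which rounds up to 90. The enrolment target of 90 for a final 80 reproduces.

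**4. Size of the effect on the contrast**

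The documents give no departure size, so 0.2-0.5 SD is assumed, with 1 SD as an outer case. "Departure" means how far the dropouts' unseen mean lies from what MAR predicts.

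- Shift in one arm's mean = (5/45) × departure.
- SE of the contrast at one visit, 40 per arm, adjusted for baseline with assumed correlation r: sqrt((2/40) × (1 - r²)) = 0.224 at r = 0 and 0.160 at r = 0.7.
- Two-sided error rate = Φ(-1.96 + b) + Φ(-1.96 - b), where b = shift/SE.

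| Pattern | Departure | Shift in contrast (SD) | Shift/SE | 5% error rate becomes |
|---|---|---|---|---|
| Equal in both arms | any | 0 | 0 | 5% |
| One arm only | 0.2 | 0.022 | 0.10-0.14 | 5.1-5.2% |
| One arm only | 0.5 | 0.056 | 0.25-0.35 | 5.7-6.4% |
| Opposite directions | 0.2 | 2 × 0.022 = 0.044 | 0.20-0.28 | 5.4-5.9% |
| Opposite directions | 0.5 | 2 × 0.056 = 0.111 | 0.50-0.70 | 7.9-10.7% |

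At 1 SD the shifts are 0.111 SD (one arm) and 0.222 SD (opposite directions).

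**The case against.** **The wording is hedged, and MAR cannot be tested.** The plan says only that no relevant violation was evident, and no data analysis could settle the matter. Both points are true. They limit the fault to an unsupported conclusion, and they are also why a stated range of departures is needed in place of a verdict.

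**GEE and EM are not offered as tests of MAR.** This stands. A reader might infer that the plan presents agreement with GEE and EM as robustness to MNAR, but the text says only that those analyses were performed. The gap remains because nothing else fills it. A reader might also infer that the difference between GEE and the mixed model is the same whether or not MAR holds. That is not so in general: it changes when dropout follows the unseen outcome, and it depends on a working correlation the plan does not state. It is simply not a test of MAR.

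**Retention effort was largely common to both arms.** This stands in part. Neither arm was coached in months 7-9. Controls had monthly manual BP and weight measures in months 1-3. Both arms had three-monthly personal contact, rising gift cards and a completion bonus. A departure that differs by arm is possible, not established.

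**The seven early leavers raise a different question.** Largely true. A reader might infer that randomised women were dropped from the analysis. Randomisation followed the CDSMP, so some may have been randomised, but the plan does not say. It also uses baseline in a post-CDSMP sense in one place, which leaves the timing of the first post-CDSMP visit unclear.

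**Scope.** The plan's missing-data text speaks of variables and items, while the figures above treat dropout only.

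**Conclusion.** The point holds as a fault of support. The stated rule turns evidence against MCAR into a finding of MAR, the only MNAR check cannot be reproduced, and no sensitivity analysis goes beyond the assumption on which the main models rest. A reader might go further and infer that MAR fails or that the treatment estimates are biased. The documents do not support that: they give no dropout by arm, no reasons for leaving and no outcome data.

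The likely size is modest: at most 0.056 SD for a one-arm departure up to 0.5 SD, at most 0.111 SD for opposite departures of that size, and none for equal ones. These figures rest on the planned 5 dropouts per arm, the assumed departures, and assumed baseline correlations from 0 to 0.7. The change is worth making because it is cheap and the sentence carries the validity of the main analysis.

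**What to change.** (a) Replace the concluding sentence with: *MAR cannot be verified from the observed data; robustness to departures from MAR is judged by the delta-adjusted sensitivity analysis.* Remove the rule that association with observed factors establishes MAR.

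(b) Keep the mixed model/cLDA as the main analysis. For systolic and diastolic BP, add a delta-adjusted multiple-imputation analysis over all randomised women. Vary the shift separately by arm and in both directions over a stated range, for example 0 to 1 SD (an assumed range). Report estimates and intervals across the grid, and any tipping point. Label it post hoc, since the data have been seen. GEE and EM can stay.

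(c) Report the arm of each of the seven early leavers and whether she left before or after randomisation. Include in (b) any who left after it.

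The cost is some extra SAS programming and a few lines of text, with no new data. The downside is the post hoc label and a possibly less favourable statement on robustness.
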